### 7.2.2. Summary Measures

Mean values (descriptive, unadjusted for covariates) and conditional means from the Bayesian generalized linear (mixed) models (estimated, adjusted for covariates) will be provided for each endpoint.

### 7.2.3. Population of Interest

The secondary efficacy analyses will be based on the Efficacy analysis set population, unless otherwise specified.

## 7.2.4. Statistical Analyses / Methods

Details of the planned displays are provided in **Error! Reference source not found..**

### 7.2.4.1. Statistical Methodology Specification

Principles will follow the same procedures as the Primary Efficacy analyses (see 7.1.4.1). Three sets of analyses will be performed: the first adjusting for stratification variables, a second set adjusting for variables found to be confounding (see 7.1.4.1), and a third set focusing on the subgroup of surviving patients as of the last infusion where statistically feasible. Bayesian generalized multilevel models will evaluate the differential trajectories of each secondary endpoint as a function of treatment, time, and the interaction of treatment and time.

Additional analyses will evaluate each outcome cross-sectionally at each time point as a function of treatment. Though these analyses are exploratory in nature, and Type I Error can be less of an issue in the Bayesian context, we will evaluate the robustness of any identified effects by utilizing priors specified for the purpose of regularizing estimates. Regularization will render any identified effects more likely to demonstrate replication in future samples. Both double-exponential and the horseshoe distributed priors will provide regularization following hyper-prior distributions: Half-Student's t and Chi-square distributions respectively. Specifying the degrees of freedom for each of these hyper-priors constrains the degree of shrinkage the regularization approach can impose on coefficients. A priori we set this value at degrees of freedom = 1 for each hyper-prior as suggested by Bürkner. Priors essentially form a set of assumptions that require evaluation. As such we will evaluate a family of hyper-priors on the shrinkage parameters identified by the specified degrees of freedom for both the double-exponential and horseshoe priors. An initial random split of the data into a training set (70%) and test set (30%) will provide a basis for model building and model evaluation. Within the training set, analyses will examine both double-exponential and horseshoe priors for hyper-parameters ranging from one to at least ten degrees of freedom using k-fold cross-validation to determine the best model based as defined by the ELPD (or associated quantities including the KFOLD-IC, LOOCV-IC and WAIC). The R package "brms" contains functions for specifying each type of hyper-prior, and in combination with the R package "loo" provide facilities for k-fold cross-validation. Regarding all other model parameters (i.e. those not subject to regularization) intercepts will use ~Normal ( $\mu = 0$ ,  $\sigma^2 = 1 \times 10^3$ ) priors, level-one error variances will use ~Inverse Gamma (shape = 2.001, scale = 0.0001). Level-two variances will follow recommendations by Gelman (i.e. ~Half-T (df = 3, mean = 0, standard deviation = 10)).

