Study Design:	
This phase II, randomized, placebo-controlled, double-blind, efficacy study is designed to evaluate HB-adMSCs for the treatment of Coronavirus Disease (COVID-19).
 
The screening period, up to 7 days long for each patient, will be used to assess eligibility. Once eligibility is confirmed, the patient will be considered enrolled.
 
Upon study completion, the investigators should know whether or not HB-adMSCs are effective to treat patients with Coronavirus Disease.
 
To ensure that the drug is safe, a Medical Monitor and Data Safety Monitoring Board (DSMB) will oversee the entire study,

	review any clinically significant laboratory data, including complete blood counts, serum chemistry, imaging studies, EKGs and adverse events., serum chemistry and adverse events will be reviewed.
Selection of Patients:	
Inclusion Criteria:
 
 1. Men, and women, over 18 years of age inclusively. 2. Patient is suspected to have COVID-19 infection 3. Provides consent or consent is given by their legally authorized representative (LAR) 4. Agrees to the collection of venous blood per protocol. 
Exclusion Criteria:
 
 1. Pregnancy, lactation and those who are not pregnant but do not take effective contraceptive measures, in women of childbearing age. Absence of pregnancy will be confirmed through urine pregnancy test. 2. Patients who have participated or are participating in a clinical trial of an experimental vaccine for SARS-CoV-2 or coronavirus during the study or within 30 days. 3. Inability to provide informed consent or to comply with test requirements. 4. Any medical disease or condition that, in the opinion of the site Principal Investigator or sub-investigator, precludes study participation. Including acute, subacute, intermittent or chronic medical disease or condition that would place the subject at an unacceptable risk of injury, render the subject unable to meet the requirements of the protocol, or may interfere with the evaluation of responses or the subject's successful completion of this trial.
Planned Sample Size:	Population: 100 patients. The sample size required assumes a 15% drop-out of patients.

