- Hands must be washed with soap and water for at least 20 seconds, if soap and running water are unavailable, an alcohol-based hand rub with at least 60% alcohol will suffice this action. Always wash hands that are visibly soiled.
- Avoid touching their eyes, nose or mouth.
- Healthcare workers will wear:
 - o Disposable Gowns
 - o Gloves
 - o Disposable N95 masks.
 - o Eye/face protection (e.g., goggles, face shield)
- Surfaces where subjects have been in contact will be disinfected 70% Isopropyl Alcohol.

Pre-infusion Medication

Prior to infusion, medications will be given to the participant as a precaution. Because the drug for this study is an allogeneic product, an allergy medication such as Loratadine (10mg), will be administered. The participant will be closely monitored for any signs of allergic reaction during the infusion and during the post-infusion monitoring period. No reactions are expected.

Potential Benefits

Subjects may benefit from their participation in the study by experiencing an overall feeling of well-being. Subjects enrolled in the study will be contributing to the advancement of science and to future investigations regarding stem cells and possible therapeutic applications, including treatment of respiratory diseases, specifically COVID-19.

Statistical Analysis

Determination of Sample Size

Sample size calculation was determined based upon the anticipated demand for treatment.

Null hypothesis- Efficacy

Treatment with HB-adMSCs does not cause changes in primary and secondary endpoints (listed below) for suspected Corona Virus Disease.

Alternative hypothesis-Efficacy

The alternative hypothesis for this study is that HB-adMSC treatment does result in changes from baseline values of primary and secondary endpoints in patients with suspected Corona Virus Disease.

Null hypothesis-Safety

Treatment with HB-adMSCs results in adverse or serious adverse events and/or detrimental changes in laboratory values, vital signs, weight, X-rays, EKG, or physical examination determined to be related to the study drug.

Alternative hypothesis-Safety

HB-adMSC treatment for COVID-19 does not result in adverse or serious adverse events and/or detrimental changes in laboratory values, vital signs, weight, X-rays, EKG, or physical examination determined to be related to the study drug.

Endpoints

The endpoints measured in this study are safety and clinical efficacy.

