## 2.2. Study Design

Overview of Study Design and Key Features	
Randomized, double-blind, placebo-controlled, parallel group study	
Design Features	

• Randomized, double-blind, Placebo controlled study.

• 100 Subjects

• 2 Treatment groups

▪ Group 1 → HB- adMSCs

▪ Group 2 → Placebo

• Duration of treatment: up to 7 days, and overall study includes screening (up to 7 weeks prior to randomisation), and 4 treatment visits after randomisation scheduled at Infusion 1 (Day 0), Infusion 2 (Day 3), Infusion 3 (Day 7), and Infusion 4 (Day 10). Follow-up at day 28 (EOS).

Dosing	

• HB- adMSCs (Hope Biosciences adipose derived mesenchymal stem cells) is to be administered as an IV infusion with a dose of 100 million cells

• Placebo is to be administered as an IV infusion. Contains Saline solution 0.9%

Treatment Assignment	

• Participants will be randomised 3:2 to receive HB-adMSCs active treatment or Placebo.

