## 4. ANALYSIS POPULATIONS

Population	Definition / Criteria	Analyses Evaluated
Safety analysis set	

• All randomised subjects who received at least one dose of HB-adMSCs infusion or placebo.

• If participants receive a treatment different to their randomized treatment, they will be analysed according to the treatment actually received.

	

• Safety

• Study Population

Efficacy analysis set	

• All randomized participants who received all 4 infusions of HB-adMSCs or placebo.

• Participants will be analysed according to their randomized treatment.

	

• Efficacy

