Evaluation of posterior distributions will permit statements regarding the probability that effects of varying magnitudes exist, given the data. Specification of diffuse, neutral priors will reflect the initial uncertainty regarding effect sizes. For all generalized linear models, priors for regression coefficients will be specified as  $\sim$ Normal ( $\mu=0$ ,  $\sigma^2=1 \times 10$ ), and priors for the levels one and two error variances will be specified as  $\sim$ Half-Normal ( $\mu=0$ ,  $\sigma^2=1 \times 10^3$ ). The choice of prior distribution for level two variances will follow Gelman's recommendations from the literature. Priors for the comparison of proportions will be specified as  $\sim$ Beta ( $\alpha=1.0$ ,  $\beta=1.0$ ).

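### Exploratory cross-sectional secondary analyses: the residual-variance prior makes 95% intervals about 2 to 4% too short, and the SAP does not say which patients supply the reported effects

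*SAP*

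**What the plan says.** SAP 7.2.4.1 and 7.2.4.2 describe two layers of secondary analysis. The main layer is a longitudinal multilevel model of each endpoint on treatment, time and their interaction. It uses the available scheduled measurements, and no data split is stated for it.

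The second layer, in 7.2.4.1, is a set of additional cross-sectional models at each time point. The SAP calls them exploratory and uses shrinkage priors to test how robust any identified effect is. For this layer: "An initial random split of the data into a training set (70%) and test set (30%) will provide a basis for model building"; the sentence then names model evaluation as a second purpose. Within the training part, k-fold cross-validation chooses between double-exponential and horseshoe priors and their degrees of freedom. No criterion is given for the test part, and the data set behind the reported treatment effect is not named.

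For parameters that are not shrunk, "level-one error variances will use ~Inverse Gamma (shape = 2.001, scale = 0.0001", and level-two variances get a half-t prior. SAP 7.1.4.1, speaking of all generalized linear models, says "priors for the levels one and two error variances will be specified as" Half-Normal, with a fixed variance parameter of 1 x 10^3. Section 7.2.4.1 opens by adopting the 7.1.4.1 procedures and does not say that its own error-variance prior replaces the earlier one.

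On numbers, the Protocol synopsis has "Population: 100 patients. The sample size required assumes a 15% drop-out of patients", and the Protocol section on sample size adds "Sample size calculation was determined based upon the anticipated demand for treatment". SAP 2.2: "Participants will be randomised 3:2 to receive HB-adMSCs active treatment or Placebo". SAP 7.2.3: "The secondary efficacy analyses will be based on the Efficacy analysis set population, unless otherwise specified"; SAP 4 defines that set as "All randomized participants who received all 4 infusions of HB-adMSCs or placebo".

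**The concern.** An inverse gamma prior with a tiny scale looks uninformative, but a shape near 2 is not negligible in a trial of this size. It contributes about four degrees of freedom with essentially no sum of squares, so it pulls the residual variance towards zero and shortens the intervals. How far it does so depends on the units in which a marker is recorded, which should not influence the inference.

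The split raises a separate question. If the reported effects were estimated on 70% of an already small set, precision would be lost for no stated gain. If they come from a refit on everyone, nothing is lost. The SAP leaves this open. What is at stake is the reliability of a robustness check that covers many markers and time points.

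**Working it through.** **Inputs.** 100 patients and 15% drop-out (Protocol synopsis); 3:2 allocation (SAP 2.2); 70/30 split and Inverse Gamma with shape a = 2.001 and scale b = 0.0001 (SAP 7.2.4.1); 95% credible intervals (SAP 5.7).

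**Number analysed.** 100 x (1 - 0.15) = 85, and 85 / 0.85 = 100, so these two figures agree. The 85 is an assumption. The efficacy set requires four infusions and may be larger or smaller, so 100 and 70 are shown as well. The documents give no power or precision target to reproduce.

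**What the prior adds.** For a normal outcome with residual degrees of freedom v = n - p and residual sum of squares SS, the conditional update is

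IG(a, b) -> IG(a + v/2, b + SS/2).

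This is the same as adding 2a = 4.002 degrees of freedom with sum of squares 2b = 0.0002. The break-even residual SD is sqrt(0.0002 / 4.002) = 0.0071. The prior's 97.5th percentile for the variance is only 0.00041.

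**Effect on intervals.** Take flat coefficient priors and a residual SD well above 0.007, and compare with the t interval on v degrees of freedom:

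- width ratio = [t(0.975, v + 4.002) / t(0.975, v)] x sqrt(v / (v + 4.002))
- coverage = 2 F_v[ t(0.975, v + 4.002) x sqrt(v / (v + 4.002)) ] - 1

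Example, n = 60 and p = 2: sqrt(58 / 62.002) = 0.9672; the quantile ratio is 0.9987; the product is 0.9659, so the interval is 3.4% too short.

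| n | Width ratio, 2 coefficients | Width ratio, 10 coefficients | Coverage |
|---|---|---|---|
| 100 | 0.9797 | 0.9779 | 94.5% |
| 85 | 0.9761 | 0.9735 | 94.4% |
| 70 | 0.9708 | 0.9670 | 94.3% to 94.2% |
| 60 | 0.9659 | 0.9605 | 94.2% to 94.1% |
| 50 | 0.9588 | 0.9507 | 94.0% to 93.8% |

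The upper part of the coefficient range is realistic. SAP 5.4.1 asks for baseline plus five stratification variables; with intercept and treatment that is at least eight. A simulation of 200,000 trials with 36 v 24 normal observations gave coverage of 94.2% under this prior and 95.0% under a reference prior.

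**Dependence on units.** With v = 57, the estimated SD is multiplied by sqrt[(57 s^2 + 0.0002) / (61.002 s^2)]:

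- s = 10 or 1: 0.967
- s = 0.01: 0.984
- s = 0.007: 1.00
- s = 0.003: 1.14, so intervals are now too wide

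Recording a marker in units 1,000 times larger (s from 10 to 0.01) therefore moves the factor from 0.967 to 0.984.

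**The split.** 85 x 0.7 = 59.5 training patients (about 36 v 24) and 85 x 0.3 = 25.5 test patients.

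- SE of a standardised difference, all 85: sqrt(1/51 + 1/34) = 0.221, a 95% half-width of 0.43 SD.
- Training part only: sqrt(1/35.7 + 1/23.8) = 0.265, a half-width of 0.52 SD.
- Ratio: sqrt(1/0.7) = 1.195, whatever the number analysed. With 100 patients the split is 70/30; with 70 it is 49/21.

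**The case against.** The best defence is that these are additional exploratory analyses, that the split serves model building and evaluation, and that a refit on all patients is not excluded. That stands. The 20% larger standard error is a worst case, not a planned loss.

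Several stronger readings are tempting but not supported:

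- **That the split throws away 30% of the information on every secondary outcome.** The longitudinal models in 7.2.4.1 and 7.2.4.2 have no split, so the endpoints they cover keep an estimate from all available data.
- **That the hold-out repeats what k-fold already does.** K-fold selects the prior inside the training part; the test part can judge the selected model on unused data. Preferring k-fold over all patients at this size is a design judgement, not the correction of an error.
- **That the 25 or so test patients give underpowered treatment tests with poor intervals.** The SAP plans no treatment inference there; its stated model criterion is predictive.
- **That 7.1.4.1 and 7.2.4.1 flatly contradict each other.** The rule in 7.1.4.1 is broad, but it sits in the primary section, and the rule in 7.2.4.1 is specific to the regularised models. The text needs a statement of which prior governs.

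It is also fair to say that the prior's effect is small, that it was computed with flat rather than shrinkage coefficient priors, and that it does not reach binary, count or ordinal models, which have no such residual variance. All of this stands and limits the size of the point.

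**Conclusion.** The point holds in a limited form and is minor. For continuous outcomes on ordinary scales, the stated variance prior makes 95% credible intervals in the exploratory cross-sectional models about 2.4 to 2.7% too short at n = 85 and 3.4 to 4.0% at n = 60. Coverage is about 94.4% and 94.1 to 94.2%. The effect depends on units and reverses below a residual SD of about 0.007.

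These figures assume that the prior is placed on the variance, as written, with normal outcomes, 2 to 10 coefficients and flat coefficient priors. Under the planned shrinkage priors they are approximate.

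Separately, the SAP must say which patients produce the reported effects. If only the training part does, standard errors are about 20% larger than with all patients; with a refit on everyone there is no loss. The SAP should also say which error-variance prior governs these models. The main longitudinal secondary models are not affected by the split.

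**What to change.** In SAP 7.2.4.1:

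- Replace the inverse gamma prior with a weakly informative half-t or half-normal prior on the residual SD, scaled to each outcome, or standardise the outcomes first. State that this supersedes the 7.1.4.1 error-variance prior for these models. The 7.1.4.1 prior should not simply be carried over as if it were scale-aware: it is stated for variances, with a fixed spread.
- Choose the shrinkage prior by k-fold cross-validation over all patients in the efficacy set, and report treatment effects from the selected model fitted to all of them.

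The cost is SAP wording and somewhat less programming than the present plan. The one loss is a separate hold-out check on about 25 patients.

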#### **7.2.4.2. Data Analytic Models**

All secondary endpoint efficacy measurements available at post-baseline at scheduled measurements (Visits 2 through 5 [infusions 1 through 4] for exploratory markers and clinical labs; Visits 2 through 6 [infusion 1 through end of treatment] for chest X ray, CT scan, and ordinal scale score) will be analysed in a generalized linear mixed model. The model will predict each outcome as a function of the interaction between the fixed factors treatment group and time, controlling for lower order effects of time and treatment group. Models will control for stratification variables (see [Covariates and Other Strata](#)), and subject will be included as random effects. AEs/SAEs and AE severity will be analyzed as dichotomous outcomes (whether patient exhibited AE/SAE at any time during the study). AE/SAE attribution to study drug will be analyzed as count outcomes. All models will control for stratification variables.

